12.0 Descriptive Factors

12.1 Parameters followed for hematologic response (pick one): serum M-spike ≥ 1 g/dL and urine M-spike ≥ 200 mg/24 hours vs. serum M-spike ≥ 1 g/dL only vs. urine M-spike ≥ 200 mg/24 hours only vs. serum immunoglobulin free light chain ≥ 10 mg/dL vs. extramedullary disease only. Distinguish between SPEP measurements versus quantitative IgA measurement for serum M-spike.

12.2 Parameter followed for extramedullary disease: extramedullary plasmacytoma vs. plasma cell leukemia

13.0 Treatment/Follow-up Decision at Evaluation of Patient

13.1 Patients who are sCR, CR, VGPR, PR, or SD (or usCR, uCR, uVGPR, uPR) will continue treatment per protocol.

13.2 Patients who develop progressive disease while receiving therapy will go to the event-monitoring phase.

13.3 Patients who go off protocol treatment for reasons other than PD will go to the event-monitoring phase per Section 18.0.

13.4 Criteria for Discontinuation of Treatment

Patients may discontinue treatment for the following reasons:

- Progressive multiple myeloma
- Patient refuses further treatment on the trial
- Patient develops an intercurrent illness that precludes further participation, or requires a prohibited concomitant treatment
- The Investigator withdraws the patient in the patient's best interests
- Patient is lost to follow-up (defined as the inability to contact the patient on 3 separate occasions)
- Administrative reasons (e.g., the patient is transferred to hospice care)
- An adverse event, which in the opinion of the Investigator, precludes further trial participation

All attempts should be made to complete the End of Study procedures when the patient discontinues treatment. Patients should go to event monitoring per Section 18.0, unless the patient refuses further study participation or is lost to follow-up.

13.5 Criteria for Study Discontinuation

The study may be temporarily or permanently discontinued at any site and at any time.

Reasons for study discontinuation may include, but are not limited to, the following:

- Safety concerns
- Poor enrollment
- Non-compliance with the protocol, Good Clinical Practice guidance or other regulatory requirements by the Investigator(s)
- Request to discontinue the trial by a regulatory or health authority or an IRB
- Manufacturing difficulties/concerns

All Investigators and the requisite regulatory authorities will be notified if the study is suspended or terminated for safety reasons. In the case of such termination, the Investigator will notify the IRB.

13.6 Ineligible

A patient is deemed *ineligible* if after registration, it is determined that at the time of registration, the patient did not satisfy each and every eligibility criteria for study entry. The patient may continue treatment at the discretion of the physician as long as there are no safety concerns, and the patient was properly registered.

If the patient discontinues treatment, the patient will go to the event-monitoring phase of the study (or off study, if applicable):

- If the patient received treatment, all data up until the point of confirmation of ineligibility must be submitted. Event monitoring will be required per Section 18.0 of the protocol.
- If the patient never received treatment, on-study material and the Off Treatment Form must be submitted. No further data submission is necessary.

13.7 Major violation

A patient is deemed a *major violation*, if protocol requirements regarding treatment in Cycle 1 of the initial therapy are severely violated that evaluability for primary end point is questionable. The patient may continue treatment per protocol at the discretion of the physician as long as there are no safety concerns, and the patient was properly registered. If the physician decides treatment should be discontinued, the patient will go directly to the event monitoring phase per section 18.0 and all data up until the point of confirmation of a major violation must be submitted.

13.8 Cancel

A patient is deemed a *cancel* if he/she is removed from the study for any reason before any study treatment is given. On-study material and the Off Treatment Form must be submitted. No further data submission is necessary.

14.0 Biospecimens

14.1 Summary Table of Research Blood and Biospecimens to be collected for this Protocol

Correlative Study (See Section 14.4 for more information)	Mandatory or Optional	Blood or Body Fluid being Collected	Type of Collection Tube (color of tube top)	Volume to collect per tube (# of tubes to be collected)	Study Entry	End of cycle 4	At suspected CR	At EOT	Process at site? (Yes or No)	Temperature Conditions for Storage /Shipping
Flow cytometry, GEP	Mandatory	Bone marrow aspirate	EDTA (lavender)	4 mL (2)	X	X	X	X	No	Cool Pak
Flow cytometry for adhesion molecules and circulating myeloma cells	Mandatory	Peripheral blood	EDTA (lavender)	6 mL (2)	X	X		X	No	Cool Pak
IHC, FISH	Mandatory ¹	Tissue biopsy block	Paraffin block	(1)	X				No	Ambient

¹ In patients with extramedullary soft tissue disease

14.2 Collection and Processing

14.21 Bone Marrow and Peripheral Blood for Flow Cytometry

This process will be performed on bone marrow aspirate and on peripheral blood samples following a wash no lyse method on fresh samples.

Draw 8 mL of bone marrow aspirate into two lavender top EDTA tubes. Draw 12 mL of peripheral blood into two lavender top EDTA tubes. It is important to thoroughly mix the samples with the anticoagulant agent by gently inverting the tubes not less than five times.

Samples are to be collected Monday through Thursday ONLY. Samples are to be shipped the same day they are collected. Please avoid Friday and holiday collections and shipments.

14.22 Tissue Biopsy Block for Immunohistochemistry

This procedure will be performed on paraffin embedded tissue biopsy sections.

One core of the tissue biopsy (if multiple passes made) or half of the single core should be paraffin embedded and shipped ambient. **NOTE:** Blocks are not expected to be shipped the same day as the bone marrow and peripheral blood collections.

14.3 Shipping and Handling

14.31 Flow cytometry

Immediately ship Cool-Pak via overnight delivery to the address below. A kit will be shipped to the participating site.

Please plan to obtain samples for bone marrow aspirates on Monday through Thursday only.

14.32 Immunohistochemistry

One core of the tissue biopsy (if multiple passes made) or half of the single core should be paraffin embedded and shipped.

14.33 Kits

14.331 **Kits will be used for this study** (except Mayo Clinic in Rochester will use special study cards). Kits will contain supplies and instructions for collection, processing and shipping specimens

14.332 Participating sites may obtain kits by emailing:

[REDACTED] Email requests should include address, contact information and number of kits being requested.

14.333 Kits will be sent via FedEx Ground at no additional cost to participating sites. Allow 3-4 business days to receive kits.

14.34 Shipping

Bone marrow and blood samples can be shipped with Cool Pak the same day they are collected (Monday-Thursday). They should be shipped priority overnight taking care to avoid Friday collection and shipping.

If unavoidable Friday shipping with Saturday delivery can be arranged contacting the laboratory **in advance**.

Please notify Mayo Clinic by email [REDACTED] or phone [REDACTED] to notify laboratory when specimens are being shipped.

[REDACTED]

14.4 Background and Methodology

14.41 Assessment of adhesion molecule profile: We will perform multiparametric flow cytometry on marrow and peripheral blood samples and immunohistochemistry on paraffin embedded samples. In patients with PCL, we will compare the circulating PCs with marrow PCs.

14.42 FISH studies: We will perform FISH studies on paired samples from the EMD as well as BM, examining for the common abnormalities including the IgH translocations, trisomies, p53 deletion, deletion 13 as well as chromosome 1 abnormalities. We hypothesize that p53 abnormalities and acquired abnormalities such as those involving chromosomes 1 and 13 are more likely to be found in the clone in the EMD compared with the clone present in the marrow. We also hypothesize that the genomic instability and clonal evolution form the basis of

increased risk of EMD. Patients with plasma cell leukemia will have FISH performed on the peripheral blood.

- 14.43 Gene expression profiling: We will perform GEP studies on the EMD tissue and BM samples on all patients who develop EMP and have adequate tissue/cells available. We hypothesize that the PCs in the EMD will exhibit a unique “microenvironment independence” signature suggesting the lack of continued need for the marrow microenvironment. The relative plasma cell gene expression profiles will be analyzed using high-density oligonucleotide microarrays containing probes for 50,000 transcripts and variants including 14,500 known genes (U133 Plus 2.0 array; Affymetrix, Santa Clara, CA). The arrays will be scanned using a Genechip 300 scanner and GeneChip 5.0 software (Affymetrix) will used to quantitatively analyze the scanned image. We have extensive experience with analysis. Functional analysis to determine the biological relevance of the data and to identify novel, dysregulated genes and biological pathways will be performed using a functional annotation and network mapping tool, Ingenuity Systems.
- 14.44 Microvessel density: We will estimate the microvessel density (MVD) in the paraffin embedded biopsy tissue from EMD as well as BM samples from the time of trial entry and any subsequent samples. We hypothesize that increased BM angiogenesis reflects a plasma cell clone with increased capacity to modulate the microenvironment. We also hypothesize that the EMDs with high MVD will have a poor outcome, as tumor cells are likely more resistant to treatment.

15.0 Drug Information

15.1 Ixazomib (MLN9708, Ninlaro®)

15.11 Background

Ixazomib (MLN9708) is a second-generation small molecule inhibitor of the 20S proteasome that is under development for the treatment of non-hematologic malignancies, lymphoma, and multiple myeloma.

Ixazomib (MLN2238) refers to the biologically active, boronic acid form of the drug substance, ixazomib citrate (MLN9708). The transition to MLN2238 occurs in any aqueous system.

15.12 Formulation

The ixazomib capsule drug product formulation consists of drug substance, microcrystalline cellulose, talc, and magnesium stearate. Seven different capsule strengths are manufactured: 0.2, 0.5, 2.0, 2.3, 3.0, 4.0, and 5.5 mg; each capsule strength has a unique color. Dosage strength is stated as ixazomib (the active boronic acid). Ixazomib (MLN9708) capsules are individually packaged in blisters.

Matching placebo capsules have been manufactured for the 2.3, 3.0, 4.0, and 5.5 mg ixazomib (MLN9708) capsules. The placebo capsules contain microcrystalline cellulose, talc, and magnesium stearate and are identical in color and size to the corresponding active dose.

15.13 Preparation and storage

Ixazomib (MLN9708) capsules (0.2 mg, 0.5 mg, 2 mg), individually packaged in blisters, can be stored at 2°C to 8°C or “Do not store above 25°C. Do not freeze.” Ixazomib capsules (2.3 mg, 3 mg, 4 mg, and 5.5 mg), individually packaged in blisters, can be stored at “2°C - 8°C” or “Do not store above 25°C. Do not freeze.”

Ixazomib that is dispensed to the patient for take-home dosing should remain in the blister packaging until the point of use. The investigative site is responsible for providing the medication to the patient in the correct daily dose configurations. Capsules should remain in the blisters until the point of use. Ixazomib capsules must be administered as intact capsules and must not be opened or manipulated in any way. Comprehensive instructions should be provided to the patient in order to ensure compliance with dosing procedures. Patients will be instructed to store the medication in the refrigerator until the time of use. Reconciliation will occur accordingly when the patient returns for their next cycle of therapy. Returned unused capsules should be discarded in a proper biohazard container.

Ixazomib is an anticancer drug. As with other potentially toxic compounds, caution should be exercised when handling ixazomib. It is recommended to wear gloves and protective garments during preparation when dispensed in clinic. Please refer to published guidelines regarding the proper handling and disposal of anticancer agents.

15.14 Administration

Ixazomib (MLN9708) capsules must be administered as intact capsules and are not intended to be opened or manipulated in any way. Capsules should be taken on an empty stomach with approximately 8 oz (1 cup) of water at least 1 hour before or at least 2 hours after food.

Ixazomib should not be taken if the patient has had a serious allergic reaction to boron or boron containing products.

15.15 Pharmacokinetic information

a) Absorption: After oral dosing, ixazomib is rapidly absorbed with a median T_{max} of 1 hour. The lack of a discernible relationship between BSA and ixazomib clearance over a relatively wide BSA range (1.4-2.6 m²) indicates that total systemic exposure (AUC) following fixed dosing should be independent of the individual patient's BSA. A high-fat meal decreased both the rate and extent of absorption. Therefore, ixazomib should be administered on an empty stomach.

b) Distribution: The steady state volume of distribution is large and is estimated to be 543 L. Ixazomib is 88-94% protein bound.

c) Metabolism: Metabolism is the primary route for elimination of ixazomib by both CYP and non-CYP enzymes. CYP3A4 and 1A2 comprise the major CYP isozymes that contribute to ixazomib metabolism.

d) Excretion: The mean terminal half-life is 9.5 days. Renal elimination is a minor clearance pathway for ixazomib. Dosing adjustment is not required in patients with mild and moderate renal impairment in studies.

However, in a dedicated renal impairment study (C16015), unbound AUC0-last was 38% higher in patients with severe renal impairment or end-stage renal disease (ESRD) requiring dialysis as compared to patients with normal renal function. Accordingly, a reduced starting dose of ixazomib is recommended in patients with severe renal impairment and ESRD requiring dialysis. Unbound systemic exposures of ixazomib are 27% higher in patients with moderate or severe hepatic impairment as compared to patients with normal hepatic function. A reduced starting dose of ixazomib is recommended for patients with moderate or severe hepatic impairment.

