3.0 Patient Eligibility

3.1 Registration - Inclusion Criteria

- 3.11 Age ≥ 18 years.
- 3.12 Previously treated myeloma, currently with extramedullary disease (defined as plasmacytoma outside bone marrow that is not contiguous with a bone lesion) with at least one lesion that has a single diameter of ≥ 2 cm or plasma cell leukemia (defined as circulating plasma cells exceeding 5% of peripheral blood leukocytes or $0.5 \times 10^9/L$ or 200 cells/150000 events by flowcytometry).
- 3.13 The following laboratory values obtained ≤ 14 days prior to registration.
- Calculated creatinine clearance (using Cockcroft-Gault equation below)* ≥ 30 mL/min
 - Absolute neutrophil count (ANC) $\geq 1000/mm^3$
 - Platelet count $\geq 50,000/mm^3$
 - Hemoglobin ≥ 8.0 g/dL

*Cockcroft-Gault Equation:

$$\text{Creatinine clearance for males} = \frac{(140 - \text{age})(\text{actual body weight in kg})}{(72)(\text{serum creatinine in mg/dL})}$$

$$\text{Creatinine clearance for females} = \frac{(140 - \text{age})(\text{actual body weight in kg})(0.85)}{(72)(\text{serum creatinine in mg/dL})}$$

- 3.14 Patients with measurable disease defined as at least one of the following:
- For patients with EMD measurable disease by CT or MRI or the CT portion of the PET/CT: Must have at least one lesion that has a single diameter of ≥ 2 cm. Skin lesions can be used if the area is ≥ 2 cm in at least one diameter and measured with a ruler.
 - Plasma cell count $\geq 0.5 \times 10^9/L$ or 5 percent of the peripheral blood white cells
 - Plasma cell count if determined by flow cytometry, $\geq 200/150,000$ events
- 3.15 ECOG performance status (PS) 0, 1 or 2 ([Appendix I](#)).
- 3.16 Provide informed written consent.
- 3.17 Negative pregnancy test done ≤ 7 days prior to registration, for women of childbearing potential only.
- 3.18 All study participants must be registered into the mandatory POMALYST REMS™ program, and be willing and able to comply with the requirements of the POMALYST REMS™ program.
- 3.19a Willing to return to enrolling institution for follow-up (during the Active Monitoring Phase of the study).
- 3.19b Willing to provide bone marrow and blood samples for correlative research purposes (see Sections 6.12 and 14.1).

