3.2 Registration - Exclusion Criteria

- 3.21 Other malignancy requiring active therapy.
EXCEPTIONS: Non-melanoma skin cancer, DCIS or carcinoma-in-situ of the cervix.
NOTE: If there is a history or prior malignancy, they must not be receiving other specific treatment for their cancer.
- 3.22 Any of the following because this study involves an investigational agent whose genotoxic, mutagenic and teratogenic effects on the developing fetus and newborn are unknown:
- Females of childbearing potential (FCBP)[†] must have a negative serum pregnancy test with a sensitivity of at least 50 mIU/mL within 10 – 14 days prior to and again within 24 hours prior to prescribing pomalidomide for Cycle 1 (prescriptions must be filled within 7 days as required by RevAssist), and must either commit to continued abstinence from heterosexual intercourse or begin TWO acceptable methods of birth control, one highly effective method and one additional effective method.
AT THE SAME TIME, at least 28 days before she starts taking pomalidomide FCBP must also agree to ongoing pregnancy testing. Men must agree to use a latex condom during sexual contact with a FCBP even if they have had a successful vasectomy.
See [Appendix IV](#): Pomalidomide Education and Counselling Guidance Document. Patient must follow pregnancy testing requirements as outlined in the POMALYST REMS™ program.
 - Nursing women
 - Men or women of childbearing potential who are unwilling to employ adequate contraception
- 3.23 Other co-morbidity which would interfere with patient's ability to participate in trial, e.g. uncontrolled infection, uncompensated heart or lung disease.
- 3.24 Other concurrent chemotherapy, radiotherapy, or any ancillary therapy considered investigational.
NOTE: Bisphosphonates are considered to be supportive care rather than therapy, and are thus allowed while on protocol treatment.
- 3.25 Patient has \geq Grade 3 peripheral neuropathy, or Grade 2 with pain on clinical examination during the screening period.
- 3.26 Major surgery \leq 14 days before study registration.
- 3.27 Systemic treatment with strong CYP3A4 inducers (e.g. rifampin, rifapentine, rifabutin, carbamazepine, phenytoin, phenobarbital, Gingko biloba, St. John's wort) within 7 days before registration.

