[†] A female of childbearing potential is a sexually mature woman who: 1) has not undergone a hysterectomy or bilateral oophorectomy; or 2) has not been naturally postmenopausal for at least 24 consecutive months (i.e., has had menses at any time in the preceding 24 consecutive months).

- 3.28 Evidence of current uncontrolled cardiovascular conditions, including cardiac arrhythmias, congestive heart failure, angina, or myocardial infarction within the past 6 months. Note: Prior to study entry, any ECG abnormality at screening must be documented by the investigator as not medically relevant.
- 3.29a QTc >470 milliseconds (msec) on a 12-lead ECG obtained during the Screening period.
Note: If a machine reading is above this value, the ECG should be reviewed by a qualified reader and confirmed on a subsequent ECG.
- 3.29b Known human immunodeficiency virus (HIV) positive.
- 3.29c Known hepatitis B surface antigen-positive status, or known or suspected active hepatitis C infection.
- 3.29d Any serious medical or psychiatric illness that could, in the investigator's opinion, potentially interfere with the completion of treatment according to this protocol.
- 3.29e Known allergy to any of the study medications, their analogues or excipients in the various formulations.
- 3.29f Known GI disease or GI procedure that could interfere with the oral absorption or tolerance of ixazomib including difficulty swallowing.
- 3.29g Diarrhea >Grade 1, based on the NCI CTCAE grading, in the absence of antidiarrheals.

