4.0 Test Schedule

Tests	Days Prior to Registration		Day 8, 15, 22 (Cycles 1-3), Day 15 (Cycle 4 onwards) ¹	Every cycle, pre- treatment ¹	End of Cycle 4 ¹	End of Treatment (+/-14 days) ¹
	≤30 days	≤14 days				
Complete medical history	X					
Adverse Event monitoring		X		X ¹⁶		X
Physical exam, including weight and vital signs		X		X ¹⁶		X
Height		X				
Performance status (ECOG scale)		X		X ¹⁶		X
CBC with differential		X	X	X ¹⁶		X
Chemistry group: sodium, potassium, glucose, alkaline phosphatase; Total and Direct bilirubin; SGOT (AST); serum creatinine, calcium, magnesium		X		X ¹⁶		X
LDH, Beta ₂ -microglobulin, C-reactive protein	X					
Electrophoresis of serum and urine (SPEP/UPEP)		X		X ^{3,16}		X ³
Affected immunoglobulin ²		X		X ^{2,16}		X ²
Immunofixation serum and urine	X			X ^{4,16}		X ⁴
Immunoglobulin free light chain (MML panel)		X		X ^{5,16}		X ⁵
X-ray skeletal survey or low dose full body CT ⁶	X			X ⁶		X
Physical measurement (EMD lesion) ⁷		X		X		
CT Scan, PET/CT, or MRI for measurement of EMD lesion ⁸	X			X ⁸		
Circulating plasma cell assessment (flow cytometry or peripheral smear) ⁹		X		X ^{9,16}		
Bone marrow aspirate and biopsy, myeloma FISH, metaphase cytogenetics, plasma cell proliferation, and flow cytometry	X			X ¹⁰	X ¹⁰	X
Biopsy of extramedullary lesion ¹¹	X					
Chest x-ray	X					
Serum pregnancy test ¹²		X ¹²				
ECG, 12 lead with interpretation	X					
Register patient for POMALYST REMS™ program ¹³		X ¹³				
Patient Medication Diary (Appendix II) ¹⁴				X	X	X
Mandatory tissue block ¹¹	X					
Mandatory Research Bone marrow sample ^R	X			X ¹⁰		X
Mandatory Peripheral Blood sample ^R	X			X ¹⁵		X ¹⁵

Cycle = 28 days {FOOTNOTES CONTINUE ON NEXT PAGE}

- 1) All scheduled visits will have a window of ± 7 days unless otherwise stated.
Note: Baseline labs can be used for Cycle 1, Day 1.
 - 2) Affected immunoglobulin refers to the baseline M-protein type, that is, IgG, IgA, or IgD. Not applicable if patient “non-secretory” or if patient has no heavy chain, i.e. light chain myeloma. Affected immunoglobulin is required after baseline only if it used for disease monitoring instead of SPEP (e.g. IgA myeloma).
 - 3) Urine Electrophoresis required only if used to assess disease response.
 - 4) Immunofixation (IF) needed only in the absence of M-protein to document sCR or CR.
 - 5) Serial light chain required if it is used for disease monitoring (measurable disease at baseline)

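### The reduced ixazomib starting dose that Section 15.15 recommends in moderate or severe hepatic impairment is not carried into eligibility or the dosing tables

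*Combined protocol and SAP*

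**What the plan says.** Section 15.15 (Pharmacokinetic information) names metabolism as the main elimination route for ixazomib. On the liver it reports: "Unbound systemic exposures of ixazomib are 27% higher in patients with moderate or severe hepatic impairment", compared with normal hepatic function, and then: "A reduced starting dose of ixazomib is recommended for patients with moderate or severe hepatic impairment". It gives no milligram value and does not define the impairment categories. The same paragraph has a parallel renal statement: "a reduced starting dose of ixazomib is recommended in patients with severe renal impairment and ESRD requiring dialysis".

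The operational sections read as follows.

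- **Inclusion 3.13** limits creatinine clearance (30 mL/min or more), neutrophils, platelets and hemoglobin. It contains no liver test.
- **Exclusion 3.29c** is the only criterion that concerns the liver, and it covers viral infection: "Known hepatitis B surface antigen-positive status, or known or suspected active hepatitis C infection".
- **Exclusions 3.23 and 3.29d** are general: "Other co-morbidity which would interfere with patient's ability to participate in trial" and "Any serious medical or psychiatric illness that could, in the investigator's opinion, potentially interfere with the completion of treatment".
- **Section 4.0** schedules a chemistry group within 14 days before registration and before each cycle. It includes "Total and Direct bilirubin; SGOT (AST); serum creatinine, calcium, magnesium".
- **Table 7.1** gives ixazomib 4 mg on days 1, 8 and 15. **Table 8.1** has the same 4 mg start, then 3 mg, 2.3 mg, 2.3 mg on days 1 and 15, and discontinuation. Neither has a hepatic qualifier, and the steps down are triggered by adverse events.

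**The concern.** The protocol contains a safety recommendation about the first dose, but the tables from which sites prescribe do not reflect it. A patient with moderate or severe hepatic impairment can meet every numeric criterion and, if dosed from the tables, starts at 4 mg. The dose then falls only after toxicity has occurred. Section 15.15 gives a mean terminal half-life of 9.5 days and dosing is weekly, so excess exposure clears slowly once a dose is omitted.

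An investigator who does follow 15.15 has no dose level to use and departs from Table 7.1 in Cycle 1, with nothing in the protocol to say that this is intended. The bilirubin and AST results that could prompt a lower start are collected before registration, but no rule uses them.

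What is at stake is the tolerability of the first cycles for any such patient, not the trial's inference.

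**Working it through.** **Step 1. Look for a rule.** The table compares what 15.15 calls for with what each operational section provides.

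| Section | Liver threshold? | Reduced start? |
|---|---|---|
| 3.13 laboratory limits | No | No |
| 3.29c viral hepatitis | No | No |
| 3.23 and 3.29d general exclusions | No, judgement only | No |
| 4.0 test schedule | Tests drawn, no limit | No |
| Table 7.1 | No | No, 4 mg only |
| Table 8.1 and Section 8 | No | No, adverse events only |

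The renal statement at least has a numeric floor on renal function in 3.13. Since 15.15 gives no cut-off for severe renal impairment either, the contrast is only that renal function is limited at entry and liver function is not.

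**Step 2. Size of the excess.** Inputs: 27% (15.15), 4 mg (Tables 7.1 and 8.1), and the dose equivalences in the Table 1-1 footnote (4.0 mg is about 2.23 mg/m², 5.5 mg about 2.97 mg/m²). The 27% itself cannot be reproduced, because the underlying data are not in the documents. Assumptions: exposure is proportional to dose, the 27% is a comparison at equal dose, and the single figure applies to both impairment categories.

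- Normal-function equivalent of 4 mg: 4 × 1.27 = 5.08 mg.
- Against the 4.0 mg recommended phase 2 dose of C16005, on which Section 7.2 bases the dose: 5.08 / 4 = 127%.
- Against the 2.97 mg/m² weekly MTD of C16004 and C16005: 5.08 / 5.5 = 92% on the fixed-dose scale. On the body-surface scale, 2.23 × 1.27 = 2.83 mg/m², and 2.83 / 2.97 = 95%.
- Table 1-1 also lists lower MTDs, which 5.08 mg exceeds: 4.0 mg in C16007 (AL amyloidosis) and 3.0 mg in C16006 (with melphalan and prednisone). It gives none with pomalidomide.

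**Step 3. Which existing level fits.** The dose that matches the intended exposure is 4 / 1.27 = 3.15 mg.

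| Starting dose | Normal-function equivalent | Share of intended exposure |
|---|---|---|
| 4 mg | 5.08 mg | 127% |
| 3 mg | 3 × 1.27 = 3.81 mg | 95% |
| 2.3 mg | 2.3 × 1.27 = 2.92 mg | 73% |

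Table 1-1 shows that the hepatic study, C16018, used 2.3 mg in moderate and 1.5 mg in severe impairment. Those are doses investigated, not the recommendation in 15.15, and 1.5 mg is not a level in Table 8.1.

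**Step 4. Effect on the statistics.** The decision rule in 16.21 (stop at 2 or fewer of 10, promising at 10 or more of 27) does not depend on the starting dose. Exact binomial calculation gives a significance level of 0.0994 and power of 0.9036, against the stated 0.10 and 0.90. The fix changes neither. One affected patient alone cannot reach the 2-of-6 threshold in 16.4 or the 5-of-15 threshold in 16.52.

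**The case against.** The strongest reply is that the recommendation is already in the protocol. Section 15 holds other conditional dosing advice that the tables do not repeat: 15.26 calls for halving pomalidomide with strong CYP1A2 inhibitors, and Tables 7.1 and 8.1 do not mention that either. This stands. A reader might infer that the protocol gives two conflicting dosing orders, or that it ignores the liver altogether. The documents support neither. One section makes a recommendation, and the sections that set eligibility and dose do not carry it forward.

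A second reply is that 3.23 and 3.29d would keep such patients out. They might. But they rest on judgement, set no liver threshold, and concern exclusion, whereas 15.15 envisages treatment at a lower dose.

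A third reply is that the excess is modest and monitored. Blood counts are taken on days 8, 15 and 22 of Cycles 1 to 3, the modification tables bind strictly for two cycles, and accrual pauses after six patients. This also stands and limits the harm. These measures act only after the higher dose has been given.

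Finally, the documents contain neither the impairment categories nor the reduced dose, so the correction cannot be completed from them alone. That is true and limits what can be specified here.

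**Conclusion.** The gap is real and narrow. An eligible patient with moderate or severe hepatic impairment who is dosed from the tables starts at about 127% of the intended unbound exposure. This rests on the three assumptions in the working: dose proportionality, a comparison at equal dose, and one figure for both categories.

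Two stronger readings should be resisted. A reader might infer that such patients would be dosed above the maximum tolerated dose. The equivalent of about 5.1 mg is below the weekly MTD of C16004 and C16005. It is above the MTDs of two studies in other settings, and the documents give none for this triplet, so the question stays open. A reader might also infer that a predictable share of the 30 patients is at risk. The documents give no frequency of hepatic impairment in this population, so no expected number can be stated, and it may be zero.

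Endpoints, sample size and error rates are unaffected. This is a minor patient-safety correction.

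**What to change.** Add one row to Table 7.1 and one to Table 8.1, cross-referenced to 15.15, for patients with moderate or severe hepatic impairment:

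- **Classification:** baseline bilirubin and AST, using the categories in the Investigator's Brochure.
- **Starting dose:** the existing 3 mg level, or lower if the Brochure directs. The Brochure should be checked before the level is fixed, because 3 mg is above both doses studied in C16018.
- **Remaining steps from 3 mg:** 2.3 mg, then 2.3 mg on days 1 and 15, then discontinue.

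The change needs no new test, provided the Brochure's categories use only bilirubin and AST. Its cost falls on the affected patients: two reduced levels before discontinuation instead of three. If the Brochure directs a start at 2.3 mg, exposure would be about 73% of that intended, with one reduced level left.
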